15.5 Subject Information and Informed Consent

Before any trial-related activities and in agreement with applicable regulatory requirements, the investigator must give the subject oral and written information about the trial in a form that the subject can understand. The Investigator must ensure that the subject is fully informed about the aims, procedures, potential risks, any discomforts and expected benefits of the Trial. Before consenting, the subject must be left with ample time to consider and to pose questions.

It must be emphasised that participation is voluntary and that the subject has the right to withdraw from the Trial at any time without prejudice.

The original, signed Informed Consent Forms must be kept in the Investigator File.

The subject will receive a copy of the Subject Information and his/her signed Informed Consent Form.

If new information becomes available that may be relevant to the trial subject's willingness to continue participation in the trial, a new Subject Information and Informed Consent Form will be forwarded to the IEC(s)/IRB(s) (and RAs, if required). The trial subjects will be informed about this new information and re-consent will be obtained.

15.6 Subject Confidentiality

Subject confidentiality is strictly held in trust by the participating investigators, their staff, and Hansa Biopharma and their agents. This confidentiality is extended to cover testing of biological samples and genetic tests in addition to the clinical information relating to participating subjects.

The trial protocol, documentation, data, and all other information generated will be held in strict confidence. No information concerning the trial, or the data will be released to any unauthorized third party.

The trial monitor or other authorized representatives of Hansa Biopharma may inspect all documents and records required to be maintained by the investigator, including but not limited to, medical records (office, clinic, or hospital) and pharmacy records for the subjects in this trial. The clinical trial site will permit access to such records.

16. ARCHIVING

16.1 Retention of Clinical Trial Site Documentation

The investigator is responsible for maintaining all the records, which enable the conduct of the trial at the site to be fully understood, in compliance with ICH-GCP. The trial documentation including all the relevant correspondence should be kept by the investigator for at least 25 years after the completion or discontinuation of the trial if no further instructions are given by Hansa Biopharma.

The investigator is responsible for the completion and maintenance of the confidential subject identification code which provides the sole link between named subject source records and anonymous eCRF data for Hansa Biopharma. The investigator must arrange for the retention of this Subject Identification Log and signed Informed Consent Documents for at least 25 years after the completion or discontinuation of the trial.

No trial site document may be destroyed without prior written agreement between the investigator and Hansa Biopharma. Should the investigator elect to assign the trial documents to another party, or move them to another location, Hansa Biopharma must be notified. If the investigator retires and the documents can no longer be archived by the site, Hansa Biopharma can arrange having the Investigator File archived at an external archive.

16.2 Trial Master File

Hansa Biopharma will archive the Trial Master File in accordance with ICH-GCP and applicable regulatory requirements.

Details of the changes to the protocol are shown below. Changes to the text are shown in ~~strike through~~ text and new text in *underlined italics*.

OTHER DOCUMENTS AND SYSTEM IMPACTED BY THE AMENDMENT

All study documents related to SAE/SUSAR reporting will be updated as required.

1 Change in CRO responsible for SAE/SUSAR reporting

Hansa Biopharma has changed the CRO responsible for SAE/SUSAR reporting and the protocol has been updated with the new contact details.

1.1 Section 9.2.4 Reporting of Serious Adverse Events (2nd paragraph to 5th paragraph)

Changed from:

An assigned contract research organisation (CRO), [REDACTED] will be responsible for the SAEs handling in accordance with International Conference on Harmonisation (ICH) Good Clinical Practice (GCP) and local regulations.

As soon as the investigator is aware of a potential SAE, he/she should contact [REDACTED] [REDACTED] and, in any case no later than 24 hours after the knowledge of such a case. At the time of initial reporting the investigator must provide as a minimum requirement, subject number, birth date, description of the SAE and a preliminary assessment of causality.

Contact Information:

CRO:

[REDACTED]

e-mail:

[REDACTED]

For fatal or life-threatening AEs where important or relevant information is missing, active follow-up is undertaken immediately. Investigators or other site personnel must inform the

██████████ about any follow-up information on a previously reported SAE immediately but no later than within 24 hours of when he or she becomes aware of it. The ██████████ will advise the investigator/trial site personnel how to proceed.

The SAE reporting procedures are detailed in the trial specific Safety Management Plan. This plan is an agreement between Hansa Biopharma and ██████████.

Changed to:

An assigned contract research organisation (CRO), ██████████ will be responsible for the SAEs handling in accordance with International Conference on Harmonisation (ICH) Good Clinical Practice (GCP) and local regulations.

As soon as the investigator is aware of a potential SAE, he/she should contact ██████████ ██████████ and, in any case no later than 24 hours after the knowledge of such a case. At the time of initial reporting the investigator must provide as a minimum requirement, subject number, birth date, description of the SAE and a preliminary assessment of causality.

Contact Information:

CRO: ██████████

e-mail: ██████████

For fatal or life-threatening AEs where important or relevant information is missing, active follow-up is undertaken immediately. Investigators or other site personnel must inform the ██████████ ██████████ about any follow-up information on a previously reported SAE immediately but no later than within 24 hours of when he or she becomes aware of it. ██████████ will advise the investigator/trial site personnel how to proceed.

The SAE reporting procedures are detailed in the trial specific Safety Management Plan. This plan is an agreement between Hansa Biopharma and ██████████.

1.2 Section 9.2.5 Reporting of Suspected Unexpected Serious Adverse Reactions (3rd and 4th paragraph)

Changed from:

██████████ will be responsible for ensuring reporting all SUSARs to RAs in accordance with International Conference on Harmonisation (ICH) Good Clinical Practice (GCP) and local regulations. ██████████ is also responsible for informing all participating trial investigators of any SUSARs on an expedited basis and in accordance with applicable regulations.

The SUSAR reporting procedures are detailed in the trial Safety Management Plan. This plan is an agreement between the Hansa Biopharma, and ██████████. In addition, Hansa Biopharma is responsible for informing all investigators in all other ongoing studies involving imlifidase about all SUSARs.

Changed to:

██████████ will be responsible for ensuring reporting all SUSARs to RAs in accordance with International Conference on Harmonisation (ICH) Good Clinical Practice (GCP) and local regulations. ██████████ is also responsible for informing all participating trial investigators of any SUSARs on an expedited basis and in accordance with applicable regulations.

The SUSAR reporting procedures are detailed in the trial Safety Management Plan. This plan is an agreement between the Hansa Biopharma, and ██████████. In addition, Hansa Biopharma is responsible for informing all investigators in all other ongoing studies involving imlifidase about all SUSARs.

1.3 Section 9.3 Pregnancy and Pregnancy Outcome (2nd paragraph)

Changed from:

.... A Pregnancy Report Form must be sent by the investigator to ██████████ at the latest within two weeks of learning of the pregnancy. The outcome of all pregnancies (spontaneous miscarriage, elective termination, normal birth or congenital abnormality) will be followed up on the Pregnancy Report Form even after the subject has completed or discontinued the trial. ██████████ will follow up ...

Changed to:

... A Pregnancy Report Form must be sent by the investigator to ██████████ ██████████ at the latest within two weeks of learning of the pregnancy. The outcome of all pregnancies (spontaneous miscarriage, elective termination, normal birth or congenital abnormality) will be followed up on the Pregnancy Report Form even after the subject has completed or discontinued the trial. ██████████ will follow up ...

2 Editorial changes

A few minor editorial changes were made without any implications on the study protocol and procedures.

2.4 New Section – Protocol Revision History Summary of Changes

Changed from:

-

Changed to:

Protocol Revision History including Summary of Changes

| Protocol Version | Date | Including Amendment Type and No. | Overall Rationale for Changes |
|-------------------------|--------------------|---|---|
| 1.1 | 22-NOV-2021 | Non-substantial amendment No. 01 | 
Change in CRO responsible for SAE/SUSAR reportingUpdated number of participating sites to approximately 14 |
| 1.0 | 02-OCT-2020 | N/A | Initially approved protocol |

See Appendix 1 “Clinical Study Protocol Amendment” for details of Amendment No. 01.

2.5 Section 1.1 Background (Table 1, 1st row)

Changed from:

| Trial No / EudraCT No | Phase / Subjects | Main objectives |
|--------------------------|---------------------|-----------------|
| | | |

Changed to:

| Trial No. / EudraCT No. / IND No. | Phase / Subjects | Main objectives |
|--|---------------------|-----------------|
| | | |

2.6 Section 3.3 Planned Number of Trial Sites and Subjects

Changed from:

All sites included in the feeder trial, approximately 8-11 sites, in US,.....

Changed to:

All sites included in the feeder trial, approximately 8-11/14 sites, in US,.....

2.7 Section 6.1.1 Screening (Header and 1st paragraph)

Changed from:

6.1.1 Screening (may be conducted at the earliest at the last visit in feeder trial and at the latest at Year 1 (one year after start of treatment in feeder trial +/- the visit window of 2 months)

Changed to:

6.1.1 Screening (may be conducted at the earliest at the last visit in feeder trial and at the latest at Year 1 (one year after start of treatment in feeder trial +/- the visit window of 2 months)

Screening may be conducted at the earliest at the last visit in feeder trial and at the latest at Year 1 (one year after start of treatment in feeder trial +/- the visit window of 2 months).

The following assessments and activities will be performed:

2.8 Section 6.1.2 Year 1, Year 2, and Year 3 (End-of-Trial) (Header and 1st paragraph)

Changed from:

6.1.2 The following activities and assessments will be performed at Year 1(+/-2 months), Year 2 (+/-4 months), Year 3 ((+/-4 months)and End-of-Trial)

Changed to:

6.1.1 The following activities and assessments will be performed at Year 1(+/-2 months), Year 2 (+/ 4 months), Year 3 ((+ 4 months)and End of Trial) Year 1, Year 2, and Year 3 (End-of-Trial)

The following visit windows applies:

Year 1: *(+/- 2 months)*

Year 2 and Year 3 (End-of-Trial): *(+/- 4 months)*

The following activities and assessments will be performed:

2.9 Section 6.2. Flow Chart (1st and 2nd row)

Changed from:

| Visit (post treatment in feeder trial) | Screening | Year 1 | Year 2 | Year 3 EOT |
|--|----------------------------|--------------|--------------|--------------|
| Visit window | EOT feeder trial to year 1 | +/- 2 months | +/- 4 months | +/- 4 months |

Changed to:

| Visit (post treatment in feeder trial) | Screening | Year 1 | Year 2 | Year 3 (EOT) |
|--|---------------------------------------|--------------|--------------|--------------|
| Visit window | EOT feeder trial to Year 1 | +/- 2 months | +/- 4 months | +/- 4 months |

2.10 New Section 18. Appendix 1

Changed from:

-

Changed to:

18. APPENDIX 1

18.1 Protocol Amendment 01

eGFR	estimated Glomerular Filtration Rate
FAS	Full analysis set
HLA	Human Leukocyte Antigen
HR	Heart rate
IgG	Immunoglobulin G
IMP	Investigational medicinal product
ITT	Intention-to-treat
MedDRA	Medical Dictionary for Regulatory Activities
PK	Pharmacokinetics
PP	Per-protocol
PT	Preferred term
Randomised	Patient randomised to study treatment
SAE	Serious adverse event
SAP	Statistical analysis plan
Screened	Patient who enters the screening phase of the study
SD	Standard deviation
SOC	System organ class
Sqrt	Square root
STDM	Study data tabulation model
TLF	Tables, listings and figures
T _{max}	Time of observed C _{max}
T _{½ el}	Elimination half-life

1 Introduction

This document describes the planned statistical analyses for 20-HMedIdeS-18 which will include data processing, data analyses and data presentation. This Statistical Analysis Plan (SAP) is based on protocol version 2.1_AUT_22Nov2021 (for Austria), protocol version 1.1 (for France) and protocol version 3.0_DEU (for Germany) (Doc. No.: 2020-059).

1.1 Study objectives and endpoints

1.1.1 Objectives

As stated in the protocol the primary objective of this trial is:

- To evaluate kidney graft survival in patients that have been treated with imlifidase or plasma exchange in association with Antibody Mediated Rejection (AMR) in the trial 16-HMedIdeS-12 (referred to as the feeder trial).

As stated in the protocol the secondary objectives of this trial are to:

- Evaluate overall graft survival at Year 1 and 2
- Evaluate patient survival at Year 3
- Evaluate kidney function at Year 1, 2 and 3
- Evaluate Donor Specific Antibody (DSA) levels at Year 1, 2 and 3
- Evaluate anti-imlifidase Immunoglobulin G (IgG) levels at Year 1, 2 and 3
- Investigate the occurrence of AMR episodes after completion of the feeder trial (classified according to Banff 2017 or later version)
- Investigate the occurrence of other graft rejection episodes (classified according to Banff 2017 or later version)

1.1.2 Endpoints

The primary endpoint of this trial is:

- To evaluate the overall graft survival at Year 3.

Secondary endpoints of this trial are:

- Overall graft survival evaluated at Year 1 and 2.
- Patient survival, evaluated at 3 years after start of treatment in feeder trial.
- Kidney function, as evaluated by estimated Glomerular Filtration Rate (eGFR), S/P-creatinine and albumin/creatinine ratio in urine at 1, 2, and 3 years after start of treatment in feeder trial.
- Proportions of patients with presumed or biopsy proven AMR episodes (classified according to Banff 2017 or later version) within 3 years after start of treatment in feeder trial.
- Proportion of patients with presumed or biopsy-proven rejection episodes, (other than AMR episodes) (classified according to Banff 2017 or later version) up to 3 years after start of treatment in feeder trial.

- DSA levels at 1, 2, and 3 years after start of treatment in feeder trial.
- Anti-imlifidase IgG at 1, 2, and 3 years after start of treatment in feeder trial.

[figure not shown]
2 Study design

The study is an observational 3-year follow up trial after the 16-HMedIdeS-12 study. The purpose of this trial is to investigate the long-term outcomes of imlifidase or plasma exchange treatment on active or chronic active AMR in kidney transplant recipients. The long-term outcomes are evaluated by considering the overall graft survival, patient survival, kidney function, DSA levels, AMR episodes, and anti-imlifidase IgG.

A maximum of 30 patients can be included depending on patients' willingness to participate in the trial after the 16-HMedIdeS-12 study.

The flow of the study is displayed in Figure 1 below.

Figure 1.

2.1 Overview of study procedures

Screening

Screening may be conducted at the earliest at the last visit in the feeder trial and at the latest at Year 1 (one year after start of treatment in the feeder trial +/- the visit window of 2 months).

These assessments and activities are performed:

- Check inclusion and exclusion criteria.
- Sign informed consent.
- Assessment of graft survival. For patients with graft loss after last visit in the feeder trial, date, reason for graft loss, medical history, and root cause will be recorded.
- Record patient survival (if applicable, date and cause of death).
- Pregnancy test (only for Austrian patients due to an exclusion criterion in the protocol version 2.1_AUT_22Nov202 regarding “Lactating or pregnant females”).

At Year 1, Year 2, and Year 3 (End-of-Trial)

The following visit windows applies:

Year 1: (+/- 2 months)

Year 2 and Year 3 (End-of-Trial): (+/- 4 months)

The following activities and assessments will be performed:

- Assessment of graft survival. For patients with graft loss since last visit in the feeder trial or screening (if screening is done at a separate visit), date, reason for graft loss, medical history, and root cause will be recorded.
- Record patient survival (if applicable, date and cause of death).
- Collect information about graft rejection episodes, (classified by Banff 2017 or later). For-cause biopsies together with contemporaneous local DSA analyses, kidney function parameters (P-creatinine, U-albumin/creatinine ratio) and treatments (e.g. plasma exchange and IVIg) will be collected to assess the rejection episodes.
- Record information from standard of care biopsies, if available.
- Sample for S/P-creatinine will be drawn (eGFR will be calculated by the Sponsor)
- Collect urine sample for measurement of albumin/creatinine ratio.
- Sample for HLA antibodies, including DSA, and ADA will be drawn.
- Record comorbidity such as infections, malignancy, diabetes mellitus, cardiovascular events and comorbidity leading to worsening of kidney function, that occurred after end of trial in feeder trial.
- Record current immunosuppressive medications.
- Record treatment with dialysis.
- AEs related to trial procedure or IMP in feeder trial will be recorded.

The study flow chart is displayed in Table 1.

Table1. Flow chart.

Visit (post treatment in feeder trial)	Screening	Year 1	Year 2	Year 3 (EOT)
Visit window	EOT feeder trial to year 1	+/- 2 months	+/- 4 months	+/- 4 months
Assessment				
Informed consent	x ¹			
Inclusion and exclusion criteria	x ¹			
Enrolment and allocation of patient no	x ¹			
Pregnancy test	x ⁶			
Graft survival status	x	x	x	x
Patient survival status	x	x	x	x
Graft rejection episodes ²		x	x	x
Kidney graft biopsy reports ³		x	x	x
S/P-creatinine, eGFR calculation (performed by Sponsor)		x	x	x
U-Albumin/creatinine ratio		x	x	x
Sample for HLA antibodies, including DSA (donor-specific antibodies) and ADA (Anti-imlifidase IgG) central lab		x	x	x
Comorbidity ⁴		x	x	x
Current immunosuppressive medication		x	x	x
Treatment with dialysis		x	x	x
Adverse events related to trial procedure or IMP in feeder trial ⁵		x	x	x

Footnotes

- ¹⁾ Signing of Informed consent and check of inclusion and exclusion criteria can be done any time between end of trial in feeder trial and at year 1 or at year 1.
- ²⁾ Record graft rejection episodes (classified by the Banff 2017 or later version), creatinine and DSAs taken in standard of care due to the episode and treatments (e.g. plasma exchange and IVIg).
- ³⁾ If standard of care kidney biopsies are collected for any reason, at any time-point, e.g. suspected graft rejections, record information in the eCRF.
- ⁴⁾ Record comorbidity that are medically relevant and registered in the patient's medical record. Medically relevant comorbidity are infections, malignancy, diabetes mellitus, cardiovascular events and comorbidity leading to worsening of kidney function.
- ⁵⁾ Only Adverse events caused by a procedure in the protocol (e.g. blood sampling) or related to IMP in feeder trial will be recorded.
- ⁶⁾ Only for Austrian patients.

2.2 Determination of sample size

No calculation for the sample size is made. The 30 patients included in the feeder trial (16-HMedIdeS-12) are considered and asked if they want to participate in this trial. Therefore, the sample size will be 30 as maximum.

2.3 Blinding

The study is an open-label study. The study is fully unblinded.

2.4 Data pre-processing

The export data sets from data management will be transformed into Study Data Tabulation Model (SDTM) structure and format following the implementation guide version 3.2 (current version) and also following “Therapeutic Area Data Standards User Guide for Kidney Transplant Version 1.0 (Provisional)”. Analysis Data Model (ADaM) data sets will be prepared based on the SDTM data sets following implementation guide version 1.1 (current version). Tables, figures, and listings will be prepared from the ADaM data sets.

3 Analysis sets

3.1 Full analysis set

The Full Analysis Set will be defined as all patients enrolled in 20-HMedIdeS-18. Because of the observational nature of this trial no other analysis set will be defined, and all data presentations and all outputs will be based on the FAS.

4 Statistical analyses and presentation of data

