3. INVESTIGATIONAL PLAN

3.1 Overall Trial Design

This is an observational 3-year follow up trial. Trial sites that have participated, or are currently participating, in trial 16-HMedIdeS-12 (the “feeder trial”) will be contacted and requested to approach subjects for enrolment in the trial. Up to 30 subjects will be included depending on subjects’ willingness to participate in the trial. Subjects who lose their graft during the feeder trial or in the intermediate time before being able to enter this trial will not continue in the trial but information about the graft loss will be collected.

The trial will primarily evaluate graft survival. The subjects will attend 3 follow up visits 1, 2 and 3 years after start of treatment in the feeder trial. Signing of Informed Consent may be performed any time between last visit in the feeder trial and up to first visit in the follow up trial.

Kidney function and patient survival will be assessed. Graft rejection episodes will be determined using classification according to Banff 2017 or later version. Information from kidney biopsies performed within standard of care will be collected. Blood samples for analysis of DSA and ADA will be collected at each visit. Medically relevant comorbidity (infections, malignancy, diabetes mellitus, cardiovascular events and comorbidity leading to worsening of kidney function), will be recorded. Information about treatments of graft rejection episodes will be recorded (e.g. plasma exchange and IVIg) as well as creatinine-level and DSA data conducted within standard of care due to the graft rejection episode.

If a planned visit cannot be performed, subjects may be contacted by phone and assessments described in this protocol may be collected from a local laboratory.

The overall trial outline is summarized in [Figure 1](#).

Figure 1. Overall trial design.

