7. TRIAL ASSESSMENTS

7.1 Assessments related to Primary Endpoint

The primary endpoint of this trial is to determine the overall graft survival, defined as time from start of treatment (imlifidase or plasma exchange) of active or chronic active AMR in feeder trial to graft loss, evaluated at year 3. Graft loss is defined as permanent return to dialysis for at least 6 weeks, re-transplantation, or nephrectomy. The date of graft loss will be recorded. If dialysis is used to define graft loss, the date of graft loss is the first day of the dialysis period defining the graft loss.

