12.1 Analysis Sets

12.1.1 Full Analysis Set (FAS)

The Full Analysis Set will be defined as all patients enrolled. Because of the observational nature of this trial no other analysis set will be defined and all data presentations and analyses will be based on the FAS.

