4.4.1 Primary efficacy analysis

Overall graft survival at Year 3. Graft survival is defined as time from start of treatment (imlifidase or plasma exchange) of active or chronic active AMR in feeder trial to graft loss. Graft loss is defined as permanent return to dialysis for at least 6 weeks, re-transplantation, or nephrectomy. If dialysis is used to define graft loss, the date of graft loss will be the first day of the last ongoing dialysis period reported.

The primary endpoint, overall graft survival at Year 3, will be analysed by the Kaplan-Meier survival method. The overall graft survival will be tabulated and presented graphically by treatment.

The following events will be censored at the time of occurrence: withdrawal from the trial without graft loss, evaluation time point and end of trial without graft loss.

The reason for graft loss will be tabulated by time.

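### Survival is timed from feeder-trial treatment but analysed only in later enrollees, so any graft loss or death left out before entry overstates it

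*SAP*

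**What the plan says.** - **Clock.** SAP 4.4.1: "Graft survival is defined as time from start of treatment (imlifidase or plasma exchange) of active or chronic active AMR in feeder trial" up to graft loss. Protocol 7.1 and 12.3.1 agree. Patient survival has the same time zero (Protocol 7.2.2, SAP 4.4.2.2).
- **Population.** Protocol 12.1.1: "The Full Analysis Set will be defined as all patients enrolled", and "no other analysis set will be defined and all data presentations and analyses will be based on the FAS". SAP 3.1 ties the set to the follow-up trial by name: "The Full Analysis Set will be defined as all patients enrolled in 20-HMedIdeS-18". SAP 4.4 limits the efficacy data to its participants.
- **Entry.** Consent comes before any procedure (Protocol 6.1). Screening falls between the last feeder visit and Year 1 with its 2-month window (Protocol 6.1.1). Feeder follow-up runs to 180 days (Protocol 1.1).
- **Losses before entry.** Protocol 3.1: "Subjects who lose their graft during the feeder trial or in the intermediate time before being able to enter this trial will not continue". It adds that they "will not continue in the trial but information about the graft loss will be collected".
- **Passages that point the other way.** The note in Protocol 4.2 admits dosed patients who did not complete the feeder trial. Protocol 4.3 does not list graft loss as an exclusion. Protocol 6.1.1 and 6.1.2 and SAP 2.1 record losses that occurred after the last feeder visit.
- **Analysis.** Kaplan-Meier by treatment. The listed censoring events are "withdrawal from the trial without graft loss, evaluation time point and end of trial without graft loss". Neither document has a delayed-entry, landmark or all-treated rule. SAP Table 14.2.3 reports freedom from graft loss at 1, 2 and 3 years in the Full Analysis Set.

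**The concern.** The clock starts months before a patient can join the analysis set, and under Protocol 3.1 joining depends on not yet having had the primary endpoint event. Enrollees would then contribute time at risk from day 0 over a period in which the excluded losses cannot be counted. The curve would estimate survival given a working graft at entry, yet be reported as survival from treatment. The primary objective (Protocol 2.1.1) concerns patients who were treated, not those who were treated and later enrolled.

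At stake are the primary endpoint, graft survival at Years 1 and 2, Table 14.2.3 and patient survival. Arms of 20 and 10 are anticipated, so one omitted loss moves the smaller arm about twice as far, and the display by treatment could show or hide a difference. The planned 95% intervals describe sampling variation and do not cover this error.

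**Working it through.** **1. Plan's own figures.** There is no power calculation or event rate to reproduce. The anticipated numbers are consistent: 20 + 10 = 30 (Protocol 12.6).

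**2. Entry window.** 180/30.44 = 5.9 months to 12 + 2 = 14 months, which is 5.9/36 = 16% to 14/36 = 39% of the 3-year period. Feeder non-completers could enter earlier. The earliest patients entered near month 12, because Protocol 3.2 plans the first visit one year after the first feeder treatment.

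**3. Size per excluded loss.** Let n patients be treated in an arm, k lose the graft before entry and not enrol, and c be the 3-year estimate among enrollees. The plan reports c. The value for all treated patients is (1 − k/n) × c, so the overstatement is c × k/n. This assumes that failure to enrol with a working graft is unrelated to outcome. The values of c and k are assumptions.

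| Group | c | k = 1 | k = 2 |
|---|---|---|---|
| Imlifidase, n = 20 | 0.70 | 3.5 points | 7.0 |
| | 0.80 | 4.0 | 8.0 |
| | 1.00 | 5.0 | 10.0 |
| Plasma exchange, n = 10 | 0.70 | 7.0 | 14.0 |
| | 0.80 | 8.0 | 16.0 |
| | 1.00 | 10.0 | 20.0 |
| Total, n = 30 | 0.70 | 2.3 | 4.7 |
| | 0.80 | 2.7 | 5.3 |
| | 1.00 | 3.3 | 6.7 |

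With k = 0 every entry is zero. Head-count check: 7/10 = 70.0% becomes 7/9 = 77.8% (+7.8), and 14/20 = 70.0% becomes 14/19 = 73.7% (+3.7).

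**4. Chance that it arises.** If each patient's risk of a pre-entry loss were q, the chance of at least one among 30 is 1 − (1 − q)^30: 45% at q = 2%, 79% at 5% and 96% at 10%. These rates are assumed.

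**5. Expected size under assumed survival.** If only feeder-period losses are left out, the curve tends to S(36)/S(6). For example, 0.75/0.95 = 0.789 (+3.9 points) and 0.70/0.90 = 0.778 (+7.8). If losses between feeder exit and consent are left out too, a simulation with constant hazard and entry uniform over months 6 to 14 gave:

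| True 3-year survival | Enrolled-only estimate |
|---|---|
| 0.90 | 0.926 |
| 0.80 | 0.852 |
| 0.70 | 0.773 |
| 0.60 | 0.692 |

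**6. Patient survival.** With two deaths among 10 patients, one of them before consent, 8/10 = 80.0% becomes 8/9 = 88.9% (+8.9 points).

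**7. Cross effects.** Death is not part of the graft endpoint: "Graft loss is defined as permanent return to dialysis for at least 6 weeks, re-transplantation, or nephrectomy". If a death with a working graft is censored, omitting that patient changes nothing: with a death at month 4 and three later losses among 10, both analyses give 6/9 = 0.667. Omitting a living patient who lost the graft can slightly lower patient survival: with one death, 9/10 = 0.900 becomes 8/9 = 0.889.

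**8. Check of the remedy.** For graft survival, feeder follow-up for everyone plus re-entry at consent gave simulated errors of −0.5 to +0.3 points when 10%, 30% or 50% of eligible patients did not enrol. For patient survival, censoring graft-loss patients at feeder exit is informative. With assumed mortality 3 to 5 times higher after graft loss, the estimate stayed about 0.4 to 4.6 points too high.

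**The case against.** The strongest reply is that the documents do not settle who is excluded. The Protocol 4.2 note opens entry to dosed non-completers precisely because graft survival is the objective, and 4.3 does not bar graft loss. Protocol 3.1 could mean that such a patient consents, has the loss recorded and attends no further visits. That patient would be in the Full Analysis Set with the event counted. The SAP also rests on Austrian, French and German protocol versions. Only version 1.1 is available here, and SAP 2.1 shows that the Austrian eligibility criteria differ. This stands, and it makes the finding conditional. It does not remove the gap: 6.1.1 and 6.1.2 cover only losses after the last feeder visit, and no text says that a loss known before entry makes a patient enrolled or puts the event on the curve. Screening does record date and cause of death, but consent must come first, so a death before consent has no clear route in.

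It is also fair to say that the trial is descriptive, has at most 30 patients and was terminated in January 2023 (SAP 6), and that the feeder trial itself follows graft survival to day 180. That lowers the priority. The survival estimate is nevertheless this trial's main product.

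A reader might infer that reported survival is certainly inflated, that it is inflated by well over 10 points, or that one arm is favoured. The documents support none of these. They give no counts of losses or deaths, overall or by arm, and the largest figures need high assumed early-loss rates. Selective refusal by patients with working grafts could also add bias in either direction.

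**Conclusion.** The mismatch is real: time zero is feeder treatment, the only analysis set is later enrollees, and nothing corrects for delayed entry or uses the pre-entry losses that are collected. If Protocol 3.1 is applied as worded, 3-year graft survival is overstated by about c/n per excluded loss. For c of 0.70 to 1.00 that is 7 to 10 points in a 10-patient arm and 3.5 to 5 in a 20-patient arm. It is zero if there was no such loss. Deaths before consent bias patient survival in the same way. The size rests on assumed c and event counts, and on non-enrolment with a working graft being unrelated to outcome. This should be fixed before the survival results are reported. It does not invalidate a descriptive trial.

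**What to change.** 1. Reconcile Protocol 3.1 with 4.2, 4.3, 6.1.1 and 6.1.2, for losses during the feeder trial and for losses between feeder exit and consent. State who counts as enrolled.
2. In SAP 3.1, 4.4.1, 4.4.2.1 and Table 14.2.3, add a graft-survival analysis of all feeder-treated patients by feeder arm, using feeder follow-up and the losses that Protocol 3.1 already collects. Censor non-enrolled patients with a working graft at feeder exit. Let enrolled patients re-enter the risk set at consent. Time and losses between feeder exit and consent then both fall outside the risk set, so list those losses by arm. If such patients can enrol, state one rule that counts gap losses and gap time together.
3. At minimum, and if feeder data cannot be pooled, use delayed-entry risk sets for the enrolled-only graft and patient survival curves. Label them as conditional on being event-free at the earliest entry time, not as survival from treatment, and list pre-entry losses and deaths by arm.
4. For patient survival (SAP 4.4.2.2), include feeder-period deaths. Use the known vital status of graft-loss patients where it was collected; otherwise report the estimate as likely too high.

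**Cost.** Protocol 12.1.1 allows no other analysis set, so the addition needs an amendment or a documented deviation (Protocol 13), plus SAP wording. The merge with feeder data depends on feeder consent, which these documents do not show. No new patients or visits are needed. The figures may be less favourable. Early delayed-entry risk sets are small: in simulation the curve fell to zero by month 14 in 0.6 to 1.2% of 10-patient arms and 0.3 to 0.7% of 20-patient arms.
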